7.1.1.8.2 Evaluation of Non-Target Lesions

Complete Response (CR)

Disappearance of all non-target lesions and normalization of tumor marker level. All lymph nodes must be non-pathological in size (< 10 mm short axis).

Incomplete Response/Stable Disease (SD)

Persistence of one or more non-target lesion(s) and/or maintenance of tumor marker level above the normal limits.

Progressive Disease (PD)

Appearance of one or more new lesions and/or unequivocal progression of existing non-target lesions.

7.1.1.8.3 Evaluation Response

Progression-Free Survival

Progression-free survival (PFS) is defined as the duration of time from the date of surgery to time of progression.

7.1.1.9 Information to be collected at screening

Data to be collected on patient characteristics at screening include:

- Demography (including: date of birth, age, patient initials, gender, childbearing potential, race and ethnicity, or as allowed by local regulations)
- Relevant medical history
- Diagnosis and extent of disease, including:
 - Date of diagnosis
 - Site of active disease
 - Prior antineoplastic therapies (medications, radiation, surgeries)
 - Prior and Concomitant
 - Medications, surgical and medical procedures
 - MRI

Note: All other medications taken within 28 days before the first dose of study treatment is administered must be recorded and updated on a continual basis if there is new change to the medication.

Patients will have the following performed at screening:

- Physical examination*
- Laboratory testing*:
 - Chemistry, (comprehensive metabolic panel, magnesium, phosphorus)
 - Hematology (CBC w/differential)
 - Coagulation (PT/INR, aPTT)
 - Lipid panel
 - Urinalysis
 - Serum pregnancy test (if applicable)
- Estimated glomerular filtration rate (eGFR)
- ECOG Performance Status
- 12-lead ECG
- Weight*
- Height*
- Vital signs*
- RANO assessment (see section 5.2)

*Assessments may be done at Day 1 predose as part of screening to determine eligibility. Results must be available prior to dosing to allow eligibility review by the investigator.

If assessments are available in the medical record at the investigator's site or from the patient's referring physician and are completed within the screening window, these may be utilized for eligibility review. All lab tests per protocol must be present.

7.1.1.10 Information to be collected on screening failures

A patient who signs an informed consent but fails to satisfy all eligibility criteria for any reason will be considered a screen failure.

7.1.1.11 Treatment period

Following completion of screening procedures and verifying patient eligibility, study treatment should start as soon as possible.

Patients who discontinue study treatment should be scheduled for a visit as soon as possible and within approximately 7 days after the last dose of study treatment, at which time all of the assessments listed for the EOT visit will be performed.

7.1.1.11.1 Day 1 Enrollment

The following assessments will be performed on Day 1:

- Review of surgical and medical procedures
- ECOG
- 12-lead ECG
- Collection of AEs and Concomitant medication(s)
- Screening assessments not previously collected as noted in section [7.1.1.9](#)
- Day 1 pre-dose PK sample
- Day 1 pre-dose biomarker blood sample
- Confirm eligibility prior to study drug administration
- In clinic/hospital study drug administration
- Provide the patient the following for home dosing on Days 2 and 3
 - Instructions for study medication
 - Dosing Diary
 - Symptom Diary
 - Study drug

7.1.1.11.2 Day 2 and 3

Phase 0 patients will record study drug administration in the Dosing Diary and record symptoms in the Symptom Diary.

7.1.1.11.3 Day 4

The following assessments will be performed on Day 4:

- Review of medical and surgical procedures
- Collection of AEs and Concomitant medication(s)
- Review of home dosing diary and symptom diary

- 12-lead ECG
- Trough PK Sample (Dose Levels 0-3)
- Laboratory testing (may also be performed as a pre-surgical assessment on Day 5 or Day 6):
 - Chemistry, (comprehensive metabolic panel, magnesium, phosphorus)
 - Hematology (CBC w/differential)
 - Coagulation (PT/INR, aPTT)
 - eGFR
- In clinic/hospital study drug administration
- PK blood sampling: 0.5, 1, 2, 4, 7 hours post-dose (Dose Levels 0-3)
 - *In Dose Level 4+ only, PK blood sampling will occur on Day 5 instead of Day 4.*

7.1.1.11.4 **Day 5**

- Review of medical and surgical procedures
- Collection of AEs and Concomitant medication(s)
- 12-Lead ECG (if not collected on Day 4)
- In clinic/hospital study drug administration
- Craniotomy (Day 5 for Cohort 1 & 2; Day 6 for Cohort 3)
 - PK Collection of blood, CSF and tumor
 - Biomarker tumor collection
- Dose Level 1-3: Day 5 trough/24hrs post-dose
- Dose Level 4+ only: PK blood sampling: pre, 0.5, 1, 2, 4, 6, 8 and 24 hours (Day 6) post-dose

7.1.1.11.5 **Follow-up / EOT visit**

Phase 0 patients will have a follow up visit 7-14 days after surgery (routine post-operative visit). All Phase 2 patients should be scheduled for an EOT visit within 7 (± 3) days following discontinuation of study treatment.

The following assessments will be performed at the EOT visit:

- Physical exam
- ECOG performance status
- Weight
- Vital signs
- Laboratory blood collections
 - CMP, magnesium, phosphorus
 - Hematology (CBC w/differential)
 - Urine pregnancy test (if applicable)
- 12-lead ECG
- Collection of AEs and Concomitant medication(s)
- MRI (last standard of care MRI completed)

Patients who have had a recurrence and who undergo an additional surgical procedure, may have tissue obtained and sent to the lab per Section 7.1.1.5.

7.1.1.11.6 Safety Follow Up

All Phase 0 and Phase 2 patients will have a safety follow-up phone call 30 days after last dose (± 7) days following discontinuation of study treatment.

The following assessments will be performed at the safety follow-up phone call:

- Collection of AEs and Concomitant medication(s)

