ECG (12-Lead)	X ²	X ^{2,4}		X ⁴	X ⁴	X	15 ⁵	1,15 ⁵	1 ^{5,6}	X	

Initial Version date: 10/16/2018

Revision date: 03/11/2019, 5/07/2019, 09/26/2019, 03/17/2020, 08/26/2024

	PHASE 0						PHASE 2					Survival Follow Up Call/Letter
	Screening/ Baseline	Enrollment	At Home	Pre- surgical assess- ment	Craniotomy for resection tumor resection	Phase 0 Follow - Up	Cycle 1 (28d)	Cycle 2 (28d)	Subsequent cycles (28d)	End of study treat- ment (EoT)	Safety Follow- up (phone)	
Visit Number	1	2	n/a	3	4	5	6-9	10-13	14, 15,...	Last		
Day of cycle	-28 to-1	Day 1	Day 2 & 3	Day 4	Cohort 1&2 Day 5 or Cohort 3 Day 6	Post- Operative Visit	Day of Cycle	Day of Cycle	Day of Cycle	Last	30 days after last dose	~every 3 months after safety phone call
Vital signs	X ²					X	1, 15	1, 15	1	X		
Adverse events			Continuous		first study drug administration up to 30 days after last dose of study treatment					X		
Laboratory assessments												
Hematology (CBC w/Diff)		X		X ⁷		X	15	1, 15	1	X		
Chemistry (CMP, Mg+, Phos)		X ²		X ⁷		X	15	1, 15	1	X		
eGFR ³		X ²		X ⁷								
Coagulation (PT/INR, PTT)		X ²		X ⁷								
Lipid panel		X ²								1 ⁸		
Urinalysis (dipstick) with microscopic analysis		X ²					15	1	1			
Pregnancy test (serum HCG) if applicable		X ²										
Pregnancy test (urine) if applicable						X	1	1	1	X		
Study Drug												
Drug administration		X ⁹	X ⁹	X ⁹	X ⁹		Daily Days 1-28 day cycle ¹⁰					
Review of Home Dosing Diary and Symptom Diary				X			1	1	1	X		
PK & Biomarker sample collections												
PK Blood Sampling		X		X ¹¹	X ¹¹		1, 8, 15, 22 10	1, 8, 15, 22 10				
Collection of PK CSF					X							
Collection of PK/PD Tumor tissue					X					X ¹²		
Biomarker blood collection		X ²										

1 | The most recent MRI scan available should be utilized.

	PHASE 0						PHASE 2					Survival Follow Up Call/Letter
	Screening/ Baseline	Enrollment	At Home	Pre-surgical assessment	Craniotomy for resection tumor resection	Phase 0	Cycle 1	Cycle 2	Subsequent cycles	End of study treatment (EoT)	Safety Follow-up (phone)	
Visit Number	1	2	n/a	3	4	5	6-9	10-13	14, 15,...	Last		
Day of cycle	-28 to-1	Day 1	Day 2 & 3	Day 4	Cohort 1&2 Day 5 or Cohort 3 Day 6	Post-Operative Visit	Day of Cycle	Day of Cycle	Day of Cycle	Last	30 days after last dose	~every 3 months after safety phone call

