7.1.1.12 End of Phase Disposition

At a minimum, all patients who discontinue ribociclib+everolimus treatment, including those who refuse to return for a final visit, will be contacted for safety evaluations during the 30 days ± 7 days following the last dose of treatment.

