8.1 Adverse events

8.1.1 Definitions and reporting

An adverse event is defined as the appearance of (or worsening of any pre-existing) undesirable sign(s), symptom(s), or medical condition(s) that occur after patient's signed informed consent has been obtained. Adverse Events that are not serious will be captured following first administration of study drug.

Abnormal laboratory values or test results occurring after study drug administration are adverse events only if they induce clinical signs or symptoms, are considered clinically significant, require therapy (e.g., hematologic abnormality that requires transfusion or hematological stem cell support), or require changes in study medication(s).

Information about all AEs is collected.

Except for screening failures, adverse events that begin or worsen after the first study drug administration should be recorded. Conditions that were already present at the time of informed consent should be recorded as part of medical history. Adverse event monitoring should be

continued for at least 30 days following the last dose of ribociclib+everolimus treatment. Adverse events (including lab abnormalities that constitute AEs) should be described using a diagnosis whenever possible, rather than individual underlying signs and symptoms. When a clear diagnosis cannot be identified, each sign or symptom should be reported as a separate Adverse Event.

Adverse events will be assessed according to the Common Terminology Criteria for Adverse Events (CTCAE) version 4.03.

If CTCAE grading does not exist for an adverse event, the severity of mild, moderate, severe, and life-threatening, corresponding to Grades 1 - 4, will be used. CTCAE Grade 5 (death) will not be used in this study; rather, information about deaths will be collected through the study.

The occurrence of adverse events should be sought by non-directive questioning of the patient (subject) during the screening process after signing informed consent at each visit during the study. Adverse events also may be detected when they are volunteered by the patient (subject) during the screening process or between visits, or through physical examination, laboratory test, or other assessments. As far as possible, each adverse event should be evaluated to determine:

1. The severity grade (CTCAE Grade 1-4)
2. Its duration (Start and Ongoing at End of study)

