8.2.2 Reporting

To ensure patient safety, every SAE, regardless of suspected causality, occurring after the first study drug administration and until at least 30 days after the patient has stopped treatment must be reported to Ivy Brain Tumor Center (IBTC) within 24 hours of learning of its occurrence.

Any SAE experienced after this 30 days period should only be reported if the investigator suspects a causal relationship to the treatment. Recurrent episodes, complications, or progression of the initial SAE must be reported as follow-up to the original episode within 24 hours of the investigator receiving the follow-up information. An SAE occurring at a different time interval or otherwise considered completely unrelated to a previously reported one should be reported separately as a new event.

Information about all SAEs is collected and recorded on the Serious Adverse Event Report Form; all applicable sections of the form must be completed in order to provide a clinically thorough report. The investigator must assess and record the relationship of each SAE to each specific study treatment (if there is more than one study treatment), complete the SAE Report Form, and send the completed, signed form [contact] within 24 hours of learning of its occurrence.

The original copy of the SAE Report Form must be kept at the study site.

Follow-up information is sent to the same contact(s) to whom the original SAE Report Form was sent, using a new SAE Report Form stating that this is a follow-up to the previously reported SAE and giving the date of the original report. Each re-occurrence, complication, or progression of the original event should be reported as a follow-up to that event regardless of when it occurs. The follow-up information should describe whether the event has resolved or continues, if and how it was treated, and whether the patient continued or withdrew from study participation.

If the SAE is not previously documented in the Investigator's Brochure or Package Insert (new occurrence) and is thought to be related to the treatment, IBTC may need to report the event in a MedWatch report to the FDA.

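### The safety-call window opens at Day 23 after the last dose, although adverse-event monitoring and SAE reporting must run for at least 30 days

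*Combined protocol and SAP*

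**What the plan says.** **The call.** Section 7.1.1.11.6 states: "All Phase 0 and Phase 2 patients will have a safety follow-up phone call 30 days after last dose". It then adds a window of plus or minus 7 days. AEs and concomitant medications are collected at that call. Section 7.1.1.12 repeats the timing for everyone who discontinues, including those who refuse a final visit: they "will be contacted for safety evaluations during the 30 days ± 7 days following the last dose of treatment".

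**The required period.** Section 8.1.1 says that AE monitoring should be "continued for at least 30 days following the last dose of ribociclib+everolimus treatment". Section 8.2.2 says that SAEs from the first dose "until at least 30 days after the patient has stopped treatment must be reported", whatever their suspected cause. After that period, only SAEs with a suspected causal relationship remain reportable.

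**The visit schedule.** The AE row of Table 13 (Section 7.1) shows continuous collection from "first study drug administration up to 30 days after last dose of study treatment".

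**After the call.** Sections 4.1.1 and 4.1.2 and footnote 13 of Table 13 start long-term follow-up once the call is done. Those contacts are made about every 3 months by letter or phone and gather survival data.

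**The concern.** A window with a minus side cannot by itself meet a requirement expressed as a minimum. A site that calls on Day 24 complies with Section 7.1.1.11.6 but has not observed the full period that Sections 8.1.1 and 8.2.2 require. Nothing in the protocol asks for a second contact when the call is early, and nothing scheduled later asks about AEs in a patient who has finished treatment.

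What is at stake is the completeness of the late safety record. Drug-related toxicity is a secondary endpoint (Sections 3 and 9.6), and the planned total is only about 30 patients (Section 9.7.1), so one missed late event can visibly change an AE table. Scheduled follow-up also differs between patients for a purely administrative reason.

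**Working it through.** No figure in the plan needs reproducing. The check is window arithmetic, plus a search of the schedule for any contact that would close the gap.

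**1. Limits of the call** (Sections 7.1.1.11.6 and 7.1.1.12: target 30 days, window ±7)
- Earliest compliant call: 30 − 7 = Day 23.
- Latest compliant call: 30 + 7 = Day 37.
- Allowed call days: 37 − 23 + 1 = 15. Of these, Days 23 to 29, which is 7 days, fall before Day 30.

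**2. Shortfall against the minimum** (Sections 8.1.1 and 8.2.2: at least 30 days)
- Largest shortfall: 30 − 23 = 7 days.
- As a share of the required period: 7/30 = 23%.

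**3. Other scheduled AE contacts after the last dose** (Section 7.1.1.11.5)
- Phase 0 patients who do not continue: the post-operative visit, 7 to 14 days after surgery. Section 4.1.1 puts the last dose between 1 and 25 hours before craniotomy, so this visit falls roughly 7 to 15 days after the last dose.
- Phase 2 patients: the end-of-treatment visit at 7 (±3) days after stopping, so by Day 10.
- Both come before Day 23. The call is the only scheduled AE contact that covers the later part of the 30 days.

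**4. End of the AE period on the two texts**

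| Text | AE period after last dose | If the call is on Day 23 | If the call is on Day 37 |
|---|---|---|---|
| Section 8.1.1 | at least 30 days | Days 24–30 have no scheduled contact | Days 31–37 may be collected |
| Table 13 | up to 30 days | Days 24–30 have no scheduled contact | Days 31–37 lie outside collection |

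The lower-end gap is the same on either text. The upper end depends on which text governs, and the protocol does not say.

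**5. Dependence of dose decisions on the call.** Section 6.1.3 defines DLTs over the first 5 days in Phase 0 and the first 28-day cycle in Phase 2. Neither period is defined by the date of the call.

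**The case against.** The strongest reply is that the call does not define the collection period. Section 7.1.1.12 presents its contact as a minimum. Sections 8.1.1 and 8.2.2 set the 30-day duty regardless of the call date, and Table 13 marks AE collection as continuous. Section 8.1.1 also requires AEs already detected to be followed to resolution or until judged permanent. Section 8.2.2 keeps suspected-related SAEs reportable after 30 days. Deaths are captured in any case, through Section 8.1.1 and survival follow-up of up to 5 years.

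Most of this stands, and it limits the point. A reader might infer that the call formally ends AE collection; no section says so. A reader might also infer that events after an early call necessarily go unrecorded; the documents support only that they could be missed. Nor is the call the last AE contact for every Phase 0 patient: Section 9.7.2 expects about 50% to enter Phase 2, where AE collection resumes with scheduled visits.

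The reply does not remove the gap itself. Following known events does not detect new ones, and a continuing duty without a scheduled contact relies on patients or their doctors volunteering information.

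**Conclusion.** The call window conflicts with the minimum monitoring period, and the conflict is minor. An early call can leave at most 7 of the 30 required days (23%) without a scheduled AE contact. The events at risk are non-fatal ones that start after the call and do not otherwise reach the site. The DLT and MTD rules are unaffected, as are the PK, PD, progression-free survival and overall survival endpoints; only the descriptive toxicity summary could change.

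Two further inferences are not supported:
- That the AE window itself runs from 23 to 37 days. Those are the limits of the call. Table 13 stops collection at 30 days, so the upper limit is unsettled.
- That about half of patients would fall short. An even spread of calls over the 15 days would give 7/15 = 47%, but the documents say nothing about when calls are made. The share could lie anywhere from 0% to 100%.

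The conclusion assumes that a site treats an in-window call as sufficient and makes no further contact, which the current text permits.

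**What to change.** 1. In Sections 7.1.1.11.6 and 7.1.1.12, change the call window to 30 days +7 with no minus side, so that the call falls on Days 30 to 37 and covers the whole required period.
2. Reconcile Table 13 (up to 30 days) with Section 8.1.1 (at least 30 days), so that it is clear whether an event with onset on Days 31 to 37 that is learned of at the call is to be recorded.
3. If the main AE table uses a common 30-day onset window for comparability, list later suspected-related SAEs separately. A blanket cut-off would drop events that Section 8.2.2 deliberately keeps reportable.

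**Cost.** No contact is added. The window narrows from 15 days to 8 and some calls fall slightly later. The wording change needs sponsor and IRB review under Section 11.1 and could go into the next amendment.

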7.1.1.12 End of Phase Disposition

At a minimum, all patients who discontinue ribociclib+everolimus treatment, including those who refuse to return for a final visit, will be contacted for safety evaluations during the 30 days ± 7 days following the last dose of treatment.

7.1.1.13 Criteria for patient withdrawal

Subjects/patients may withdraw at any time or be dropped from the study at the discretion of the investigator should any untoward effects occur. In addition, a subject/patient may be withdrawn by the investigator if he/she violates the study plan or for administrative and/or other safety reasons. When a subject/ patient discontinues/withdraws prior to study completion, all applicable activities scheduled for the final study visit should be performed at the time of discontinuation. Any adverse experiences which are present at the time of discontinuation/withdrawal should be followed in accordance with the safety requirements outlined in Section 8.

Subjects/patients who discontinue from the study for reasons unrelated to the study (e.g., personal reasons) will be replaced as required for the study to meet its objectives. The decision to remove a subject/patient and to replace dropouts will be made by the investigator and study statistician. The replacement will generally receive the same treatment or treatment sequence (as appropriate) as the allocation number replaced. Both the replacement and originally allocated number will be unique numbers.

Patient death will be considered as a withdrawal from the study. Patients may also be withdrawn (the physician may decide to remove the patient from any further study activity) if any of the following occur:

- Adverse event(s) (see Section 8.1)
- Drug discontinuation if their surgery is delayed by 4 or more weeks due to drug toxicity
- Disease progression
- Major protocol deviation
- Technical problems
- Physician decision
- Non-compliance with study treatment.
- Death
- Completed

Patients must be withdrawn if any of the following occur:

- Lost to follow-up
- Subject/guardian decision
- Study terminated by sponsor
- Pregnancy (Pregnancy will be followed for outcome)

7.1.1.14 Replacement policy

Patients who do not receive a minimum of 5 daily doses or who vomit within 4 hours of any dose will be replaced upon Sponsor-Investigator discretion.

7.2 Assessment types

7.2.1 PK, PD, and pharmacometabolomics assessments

As described above.

7.2.2 Safety and tolerability assessments

Adverse experiences will be graded and recorded throughout the study according to NCI-CTCAE, version 4.03. Toxicities will be characterized in terms including duration, intensity, and time to onset. Safety endpoints will include all types of adverse experiences, in addition to laboratory safety assessments, ECOG performance scale status, and vital signs.

Safety evaluation will include the following and may also be performed at any time based on the clinical judgment of the Investigator.

Screening: vital signs, physical examination (including height/weight), ECOG, tumor evaluation, ECG

Post-Treatment: vital signs, physical examination, ECOG

Laboratory safety tests (e.g., INR/PT, aPTT, complete blood count, and serum chemistries) will be obtained and assessed per routine preoperative and/or postoperative neurosurgical protocols.

7.2.2.1 Physical examination

Physical examinations will include an examination as per standard of care. The exam may include a review of general appearance, skin, neck (including thyroid), eyes, ears, nose, throat, lungs, heart, abdomen, back, lymph nodes, extremities, and a neurologic evaluation. The physical exam should be completed by appropriately licensed personnel as per institutional guidelines or as delegated by the Investigator.

